10.4.5. Reporting of SAE to GSK

SAE Reporting to GSK via Electronic Data Collection Tool

- The primary mechanism for reporting SAE to GSK will be the electronic data collection tool.
- If the electronic system is unavailable, then the site will use the paper SAE data collection tool (see next section) in order to report the event within 24 hours.
- The site will enter the SAE data into the electronic system as soon as it becomes available.
- After the study is completed at a given site, the electronic data collection tool will be taken off-line to prevent the entry of new data or changes to existing data.
- If a site receives a report of a new SAE from a study participant or receives updated data on a previously reported SAE after the electronic data collection tool has been taken off-line, then the site can report this information on a paper SAE form (see next section) or to the medical monitor by telephone.
- Contacts for SAE reporting can be found in SRM.

SAE Reporting to GSK via Paper CRF

- Facsimile transmission of the SAE paper CRF is the preferred method to transmit this information to the **Medical Monitor**.

- In rare circumstances and in the absence of facsimile equipment, notification by telephone is acceptable with a copy of the SAE data collection tool sent by overnight mail or courier service.
- Initial notification via telephone does not replace the need for the investigator to complete and sign the SAE CRF pages within the designated reporting time frames.
- Contacts for SAE reporting can be found in SRM.

10.5. Appendix 5: Contraceptive Guidance and Collection of Pregnancy Information

10.5.1. Definitions:

Woman of Childbearing Potential (WOCBP)

A woman is considered fertile following menarche and until becoming post-menopausal unless permanently sterile (see below).

If fertility is unclear (e.g., amenorrhea in adolescents or athletes) and a menstrual cycle cannot be confirmed before first dose of study intervention, additional evaluation should be considered.

Women in the following categories are not considered WOCBP

1. Premenarchal
2. Premenopausal female with 1 of the following:
 - Documented hysterectomy
 - Documented bilateral salpingectomy
 - Documented bilateral oophorectomy

For individuals with permanent infertility due to an alternate medical cause other than the above, (e.g., mullerian agenesis, androgen insensitivity), investigator discretion should be applied to determining study entry.

Note: Documentation can come from the site personnel's: review of the participant's medical records, medical examination, or medical history interview.

3. Postmenopausal female
 - A postmenopausal state is defined as no menses for 12 months without an alternative medical cause.
 - A high follicle stimulating hormone (FSH) level in the postmenopausal range may be used to confirm a postmenopausal state in women not using hormonal contraception or hormonal replacement therapy (HRT). However, in the absence of 12 months of amenorrhea, confirmation with more than one FSH measurement is required.
 - Females on HRT and whose menopausal status is in doubt will be required to use one of the non-estrogen hormonal highly effective contraception methods if they wish to continue their HRT during the study. Otherwise, they must discontinue HRT to allow confirmation of postmenopausal status before study enrollment.

10.5.2. Contraception Guidance:

 • CONTRACEPTIVES^a ALLOWED DURING THE STUDY INCLUDE:

 • Highly Effective Methods^b That Have Low User Dependency Failure rate of <1% per year when used consistently and correctly.

 • Implantable progestogen-only hormone contraception associated with inhibition of ovulation^c

 • Intrauterine device (IUD)

 • Intrauterine hormone-releasing system (IUS)^c

 • Bilateral tubal occlusion

 • Vasectomized partner 
 • Note: Vasectomized partner is a highly effective contraceptive method provided that the partner is the sole sexual partner of the woman of childbearing potential and the absence of sperm has been confirmed. If not, an additional highly effective method of contraception should be used. Spermatogenesis cycle is approximately 90 days.

 • Highly Effective Methods^b That Are User Dependent Failure rate of <1% per year when used consistently and correctly.

 • Combined (estrogen- and progestogen-containing) hormonal contraception associated with inhibition of ovulation^c 
 • oral • intravaginal • transdermal • injectable

 • Progestogen-only hormone contraception associated with inhibition of ovulation^c 
 • oral • injectable

 • Sexual abstinence 
 • Note: Sexual abstinence is considered a highly effective method only if defined as refraining from heterosexual intercourse during the entire period of risk associated with the study intervention. The reliability of sexual abstinence needs to be evaluated in relation to the duration of the study and the preferred and usual lifestyle of the participant.

a. Contraceptive use by women should be consistent with local regulations regarding the use of contraceptive methods for those participating in clinical studies.
 
b. Failure rate of <1% per year when used consistently and correctly. Typical use failure rates differ from those when used consistently and correctly.
 
c. If locally required, in accordance with Clinical Trial Facilitation Group (CTFG) guidelines, acceptable contraceptive methods are limited to those which inhibit ovulation as the primary mode of action.
 
Note: Periodic abstinence (calendar, sympto-thermal, post-ovulation methods), withdrawal (coitus interruptus), spermicides only, and lactational amenorrhoea method (LAM) are not acceptable methods of contraception. Male condom and female condom should not be used together (due to risk of failure with friction)

10.5.3. Collection of Pregnancy Information:

Female Participants who become pregnant

- Investigator will collect pregnancy information on any female participant, who becomes pregnant while participating in this study and up to 16 weeks after the last dose of study intervention.
- Information will be recorded on the appropriate form and submitted to GSK within 24 hours of learning of a participant's pregnancy.
- Participant will be followed to determine the outcome of the pregnancy. The investigator will collect follow up information on participant and neonate, which will be forwarded to GSK Generally, follow-up will not be required for longer than 6 to 8 weeks beyond the estimated delivery date.
- Any termination of pregnancy will be reported, regardless of fetal status (presence or absence of anomalies) or indication for procedure.
- While pregnancy itself is not considered to be an AE or SAE, any pregnancy complication or elective termination of a pregnancy for medical reasons will be reported as an AE or SAE.
- A spontaneous abortion (occurring at <22 weeks gestational age) or still birth (occurring at >22 weeks gestational age) is always considered to be an SAE and will be reported as such.
- Any SAE occurring as a result of a post-study pregnancy which is considered reasonably related to the study intervention by the investigator, will be reported to GSK as described in [Appendix 4](#). While the investigator is not obligated to actively seek this information in former study participants, he or she may learn of an SAE through spontaneous reporting.

Any female participant who becomes pregnant while participating will discontinue study intervention

10.6. Appendix 6: Genetics

USE/ANALYSIS OF DNA

China only: No genetic samples will be collected from participants in China.

- Genetic variation may impact a participant’s response to treatment, susceptibility, severity and progression of disease. Variable response to mepolizumab may be due to genetic determinants that impact drug absorption, distribution, metabolism, and excretion; mechanism of action of the drug; disease etiology; and/or molecular subtype of the disease being treated. Therefore, where local regulations and IRB/IEC allow, a blood sample will be collected for DNA analysis.
- DNA samples will be used for research related to mepolizumab in COPD. CCI [REDACTED]
[REDACTED]
[REDACTED]
[REDACTED]
- CCI [REDACTED]
[REDACTED]
[REDACTED].
- The sponsor will store the DNA samples in a secure storage space with adequate measures to protect confidentiality.
- The samples will be retained while research on mepolizumab for the treatment of COPD continues but no longer than 15 years after the last participant last visit or other period as per local requirements

10.7. Appendix 7: Liver Safety: Required Actions, Monitoring and Follow-up Assessments

Liver chemistry stopping criteria and required follow up assessments

Liver Chemistry Stopping Criteria	
ALT-absolute	ALT \geq 8xULN
ALT Increase	ALT \geq 5xULN but <8xULN persists for \geq 2 weeks ALT \geq 3xULN but <5xULN persists for \geq 4 weeks
Bilirubin^{1, 2}	ALT \geq 3xULN and bilirubin \geq 2xULN (>35% direct bilirubin)
INR²	ALT \geq 3xULN and INR>1.5
Cannot Monitor	ALT \geq 5xULN but <8xULN and cannot be monitored weekly for \geq 2 weeks ALT \geq 3xULN but <5xULN and cannot be monitored weekly for \geq 4 weeks
Symptomatic³	ALT \geq 3xULN associated with symptoms (new or worsening) believed to be related to liver injury or hypersensitivity
Required Actions, Monitoring and Follow up Assessments	
Actions	Follow Up Assessments

 Immediately discontinue study intervention Report the event to GSK within 24 hours Complete the liver event CRF and complete an SAE data collection tool if the event also meets the criteria for an SAE² Perform liver event follow up assessments Monitor the participant until liver chemistries resolve, stabilize, or return to within baseline (see MONITORING below) Do not restart/rechallenge participant with study treatment since restart/rechallenge is not allowed per protocol. Permanently discontinue study intervention and continue participant in the study for any protocol specified follow up assessments 	
 Viral hepatitis serology⁴ Obtain INR and recheck with each liver chemistry assessment until the transaminases values show downward trend Obtain blood sample for pharmacokinetic (PK) analysis, within 4 weeks after last dose⁵ Serum creatine phosphokinase (CPK) and lactate dehydrogenase (LDH). Fractionate bilirubin, if total bilirubin \geq2xULN Obtain complete blood count with differential to assess eosinophilia This blood sample will be sent to the central laboratory to maintain the blind while study is ongoing. Results will be provided only if unblinding of a participant's


MONITORING:
 
For bilirubin or INR criteria:
 
 • Repeat liver chemistries (include ALT, AST, alkaline phosphatase, bilirubin and INR) and perform liver event follow up assessments within 24 hours • Monitor participants twice weekly until liver chemistries resolve, stabilize or return to within baseline • A specialist or hepatology consultation is recommended 
For All other criteria:
 
 • Repeat liver chemistries (include ALT, AST, alkaline phosphatase, bilirubin and INR) and perform liver event follow up assessments within 24-72 hours • Monitor participants weekly until liver chemistries resolve, stabilize or return to within baseline 	
treatment assignment is required. Also note that the mechanism of action of mepolizumab leads to lowering of eosinophils.
 
 • Record the appearance or worsening of clinical symptoms of liver injury, or hypersensitivity, on the AE report form • Record use of concomitant medications on the concomitant medications report form including acetaminophen, herbal remedies, other over the counter medications. • Record alcohol use on the liver event alcohol intake case report form (CRF) page 
For bilirubin or INR criteria:
 
 • Anti-nuclear antibody, anti-smooth muscle antibody, Type 1 anti-liver kidney microsomal antibodies, and quantitative total immunoglobulin G (IgG) or gamma globulins. • Serum acetaminophen adduct high performance liquid chromatography (HPLC) assay (quantifies potential acetaminophen contribution to liver injury in participants with definite or likely acetaminophen use in the preceding week [James, 2009]). NOTE: not required in China • Liver imaging (ultrasound, magnetic resonance, or computerised tomography) and /or liver biopsy to evaluate liver disease: complete Liver Imaging and/or Liver Biopsy CRF forms.
---	--

1. Serum bilirubin fractionation should be performed if testing is available. If serum bilirubin fractionation is not immediately available, discontinue study intervention for that participant if ALT ≥ 3xULN **and** bilirubin ≥ 2xULN. Additionally, if serum bilirubin fractionation testing is unavailable, **record presence of detectable urinary bilirubin on dipstick**, indicating direct bilirubin elevations and suggesting liver injury.
2. All events of ALT ≥ 3xULN **and** bilirubin ≥ 2xULN (>35% direct bilirubin) or ALT ≥ 3xULN **and** INR>1.5 which may indicate severe liver injury (possible 'Hy's Law'), **must be reported as an SAE (excluding studies of hepatic impairment or cirrhosis)**; the INR threshold value stated will not apply to participants receiving anticoagulants

3. New or worsening symptoms believed to be related to liver injury (such as fatigue, nausea, vomiting, right upper quadrant pain or tenderness, or jaundice) or believed to be related to hypersensitivity (such as fever, rash or eosinophilia)
4. Includes: Hepatitis A immunoglobulin M (IgM) antibody; HbsAg and HbcAb; hepatitis C RNA; cytomegalovirus IgM antibody; Epstein-Barr viral capsid antigen IgM antibody (or if unavailable, heterophile antibody or monospot testing); and hepatitis E IgM antibody. In those with underlying chronic hepatitis B at study entry quantitative hepatitis B DNA and hepatitis delta antibody. If hepatitis delta antibody assay cannot be performed, it can be replaced with a polymerase chain reaction (PCR) of hepatitis D RNA virus (where needed) [Le Gal , 2005].
5. PK sample may not be required for participants known to be receiving placebo or non-comparator interventions. Record the date/time of the PK blood sample draw and the date/time of the last dose of study intervention prior to the PK blood sample draw on the CRF. If the date or time of the last dose is unclear, provide the participant's best approximation. If the date/time of the last dose cannot be approximated OR a PK sample cannot be collected in the time period indicated above, do not obtain a PK sample. Instructions for sample handling and shipping are in the SRM

References

Liver chemistry increased monitoring criteria with continued therapy

Liver Chemistry Increased Monitoring Criteria – Liver Monitoring Event	
Criteria	Actions

ALT \geq5xULN and $<$8xULN and bilirubin $<$2xULN without symptoms believed to be related to liver injury or hypersensitivity, and who can be monitored weekly for 2 weeks.
 
OR
 
ALT \geq3xULN and $<$5xULN and bilirubin $<$2xULN without symptoms believed to be related to liver injury or hypersensitivity, and who can be monitored weekly for 4 weeks.
	
 • Notify the GSK Medical Monitor within 24 hours of learning of the abnormality to discuss participant safety. • Participant can continue study intervention • Participant must return weekly for repeat liver chemistries (ALT, AST, alkaline phosphatase, bilirubin) until they resolve, stabilise or return to within baseline • If at any time participant meets the liver chemistry stopping criteria, proceed as described above • If ALT decreases from ALT \geq5xULN and $<$8xULN to \geq3xULN but $<$5xULN, continue to monitor liver chemistries weekly. • If, after 4 weeks of monitoring, ALT $<$3xULN and bilirubin $<$2xULN, monitor participants twice monthly until liver chemistries normalize or return to within Baseline.

10.8. Appendix 8: AEs, ADEs, SAEs, SADEs, USADEs and Device Deficiencies: Definition and Procedures for Recording, Evaluating, Follow-up, and Reporting in Medical Device Studies

- The definitions and procedures detailed in this appendix are in accordance with ISO 14155 and European Medical Device Regulation (MDR) 2017/745 for clinical device research.
- Both the investigator and the sponsor will comply with all local medical device reporting requirements for medical devices.
- The detection and documentation procedures described in this protocol apply to all GSK medical devices provided for use in the study (see Section 6.1.1 for the list of GSK medical devices).

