- j. Ensure maintenance COPD medications from the year prior to Screening Visit 1, all medications within the 3 months prior to Screening Visit 1 and all current medications are reviewed. Any medication or vaccine (including over-the-counter or prescription medicines, vitamins, and/or herbal supplements) that the participant is receiving at the time of pre-screening/screening or receives during the study must be recorded.
- k. A complete physical exam including height and weight should be conducted at Screening Visit 1. For Subsequent visits a complete physical exam including weight only should be conducted.
- l. Pulse oximetry at Screening Visit 1 only
- m. Pregnancy testing is only required for women of child bearing potential (WOCBP). An assessment must be made at Screening Visit 1 to determine child bearing potential of each female study participant
- n. A hematology sample is only collected at Screening Visit 1 for participants with no historical eosinophil count of ≥ 150 cells/ μ L in the 12 months prior to Screening Visit 0. Note: For hematology samples collected after Randomization the absolute and differential (%) values of eosinophils, lymphocytes, basophils, neutrophils and monocytes will be blinded to site staff and sponsor. However, sites will be sent total white blood counts throughout the study.
- o. Participants who entered with stable chronic Hep B or Hep C, liver chemistry labs should be assessed monthly for the first 3 months (Screening Visit 1, Day 1, Week 4, Week 8, Week 12) then every 3 months (Week 24, Week 36, Week 48 and then at Week 52 (Exit Visit), or Early Withdrawal Visit); all other participants will have liver chemistry labs done every 3 months: Screening Visit 1, Day 1, Week 12, Week 24, Week 36, Week 48 and then at Week 52 (Exit Visit) or Early Withdrawal Visit
- p. **China only:** Blood biomarker samples will **not** be collected from participants in China

- q. The genetics sample can be collected at Visit 2 or any visit after. **China only:** Genetic blood samples will **not** be collected from participants in China.

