7.1.1. Liver Chemistry Stopping Criteria

Liver chemistry stopping criteria and increased monitoring criteria have been designed to assure participant safety and evaluate liver event etiology.

Discontinuation of study intervention for abnormal liver tests is required when:

[figure not shown]
- a participant meets one of the conditions outlined in the algorithm below
- when in the presence of abnormal liver chemistries not meeting protocol-specified stopping rules, the investigator believes study intervention discontinuation is in the best interest of the participant.

Liver Chemistry Stopping Algorithm

Abbreviations: ALT = alanine transaminase; bili = bilirubin; INR = international normalized ratio; SAE = serious adverse event; ULN = upper limit of normal

Liver Chemistry Increased Monitoring Algorithm with Continued Therapy for participants with ALT ≥3xULN but <8xULN and who do not meet any liver stopping criteria

Abbreviations: ALT = alanine transaminase; bili = bilirubin; INR = international normalized ratio; SAE = serious adverse event; ULN = upper limit of normal.

Refer to [Appendix 7: Liver Safety Required Actions and Follow up Assessments](#) for required actions, monitoring and follow up assessments for any event that met liver stopping or liver monitoring criteria.

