10.3. Appendix 3: Clinical Laboratory Tests

- The tests detailed in [Table 3](#) will be performed by the central laboratory

Local laboratory results are only allowed for parasitic screening. The investigator should decide what type of laboratory test, if any, is necessary.

- Protocol-specific requirements for inclusion or exclusion of participants are detailed in Section 5 of the protocol.
- Additional tests may be performed at any time during the study as determined necessary by the Investigator or required by local regulations.
- Pregnancy Testing
 - Refer to Section 5.1 Inclusion Criteria for Screening pregnancy criteria.
- Pregnancy testing (urine) be conducted prior to each dose of study intervention and at Study Exit/Early Withdrawal Visit (4 weeks after the last dose). Note that for female participants pregnancy occurring within 16 weeks after the last dose should be reported.

Additional serum or urine pregnancy tests may be performed, as determined necessary by the Investigator or required by local regulation, to establish the absence of pregnancy at any time during the participant’s participation in the study.

Table 3 Protocol-Required Safety Laboratory Assessments

Laboratory Assessments	Parameters			
Hematology	Platelet Count Red blood cells (RBC) Count Hemoglobin Hematocrit Red Cell Distribution Width (RDW) Mean Platelet Volume (MPV)	RBC Indices: MCV MCH	WBC count with Differential: Neutrophils Lymphocytes Monocytes Eosinophils Basophils	
Clinical Chemistry ¹	Blood urea nitrogen (BUN)	Potassium	Aspartate Aminotransferase (AST)/ Serum Glutamic-Oxaloacetic Transaminase (SGOT) International normalized ratio (INR)	Total and direct bilirubin

Laboratory Assessments	Parameters			
	Creatinine	Sodium	Alanine Aminotransferase (ALT)/ Serum Glutamic-Pyruvic Transaminase (SGPT)	Total Protein
	Glucose (non-fasting]	Calcium	Alkaline phosphatase	Albumin ³
Other Screening Tests	
 • total IgE • Follicle-stimulating hormone and estradiol (as needed in women of non-childbearing potential only) • Highly sensitive urine human chorionic gonadotropin (hCG) pregnancy test (as needed for women of childbearing potential)² • Parasitic Screening (only required in countries with high-risk or for participants who have visited high-risk countries in the past 6 months). Sites should use local laboratories. 			

NOTES:

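### Participants who keep dosing with ALT 3 to <8xULN are rechecked weekly without a required INR, so the ALT ≥3xULN with INR >1.5 stop is not systematically assessed between scheduled chemistry draws

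*Protocol*

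**What the plan says.** Appendix 7 (Section 10.7) builds its stopping criteria from three analytes, ALT, bilirubin and INR, together with symptoms and the ability to monitor. One criterion is ALT at least 3xULN with INR above 1.5. Note 2 to that table makes this combination a reportable SAE (possible Hy's law), with one exception: "the INR threshold value stated will not apply to participants receiving anticoagulants".

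Once a stopping criterion is met, INR is named throughout. The follow-up column says "Obtain INR and recheck with each liver chemistry assessment until the transaminases values show downward trend". The repeat panel for criteria other than bilirubin and INR says "Repeat liver chemistries (include ALT, AST, alkaline phosphatase, bilirubin and INR) and perform liver event follow up assessments within 24-72 hours". The panel for the bilirubin and INR criteria lists the same analytes, within 24 hours.

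A separate table covers increased monitoring with continued therapy. It applies at ALT 5 to <8xULN or 3 to <5xULN, with bilirubin below 2xULN and no relevant symptoms, and it allows dosing to continue. Its weekly requirement is "Participant must return weekly for repeat liver chemistries (ALT, AST, alkaline phosphatase, bilirubin) until they resolve, stabilise or return to within baseline", followed by "If at any time participant meets the liver chemistry stopping criteria, proceed as described above". INR does not appear in its actions or its entry criteria. Section 7.1.1 restricts this pathway to participants in that ALT range "and who do not meet any liver stopping criteria".

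Appendix 3, Table 3 includes INR in the routine clinical chemistry panel. For participants without stable chronic hepatitis B or C, footnote o of the first-year schedule (Section 1.3.1) says "all other participants will have liver chemistry labs done every 3 months". Footnote g of the second-year schedule (Section 1.3.2) makes it every 6 months.

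**The concern.** The monitoring table tells sites to act whenever a stopping criterion is met, but the sample it requires each week cannot show whether the INR criterion is met. INR becomes a required repeat test only after drug has been stopped, when it can no longer inform that decision.

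The clinical stake is an INR rise that develops after the draw that found the raised ALT. It could be found late or, if it is transient, missed. A late finding delays the SAE report. It also delays the more intensive work-up that Appendix 7 sets for the bilirubin and INR criteria: repeat tests within 24 hours, twice-weekly monitoring, a recommended hepatology consultation, and imaging or biopsy.

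The statistical stake is smaller. SAP Section 4.5.3 summarises possible Hy's law cases, and one route to that definition is ALT at least 3xULN with INR above 1.5. A rise confined to the interval between scheduled draws would be absent from that summary. Efficacy, the estimand and error control are not affected.

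**Working it through.** The plan gives no figure to reproduce. The check compares the tables and then works out the delay from the protocol's own time limits.

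**Analytes, side by side**

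| Setting | ALT | AST | ALP | Bilirubin | INR |
|---|---|---|---|---|---|
| Used in a stopping criterion (Appendix 7) | yes | no | no | yes | yes |
| Weekly repeat while dosing continues (Appendix 7, monitoring table) | yes | yes | yes | yes | **no** |
| Repeat after a stop (Appendix 7, stopping table) | yes | yes | yes | yes | yes |
| Scheduled chemistry (Appendix 3, Table 3) | yes | yes | yes | yes | yes |

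INR is the only stopping analyte missing from the weekly list.

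**Scheduled draws that include INR (no hepatitis B or C)**

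- Section 1.3.1, footnote o: weeks 0, 12, 24, 36, 48, 52. Gaps: 12, 12, 12, 12 and 4 weeks.
- Section 1.3.2, footnote g: weeks 52, 76, 100, 104. Gaps: 24, 24 and 4 weeks.

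If the ALT rise is found on a scheduled sample, INR should be available at that draw. The next required INR is then usually 12 weeks away in year 1 or 24 weeks away in year 2, unless a stop comes first.

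**Persistence stops that end the window**

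Appendix 7 stops drug if ALT 5 to <8xULN persists for 2 weeks or more, or if ALT 3 to <5xULN persists for 4 weeks or more. Take the detecting draw as week 0.

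- Weekly draws with the stop decision still open = persistence limit in weeks − 1.
- Delay for an INR rise already present at week 1 = stop week − 1, plus 24 to 72 hours to the post-stop repeat.

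| Course of ALT | Stop week | Open draws without required INR | Delay from week 1 |
|---|---|---|---|
| Stays 5 to <8xULN | 2 | 2 − 1 = 1 (week 1) | 2 − 1 = 1 week |
| Stays 3 to <5xULN | 4 | 4 − 1 = 3 (weeks 1–3) | 4 − 1 = 3 weeks |
| Falls to 3 to <5xULN at week 2, clock restarts | 2 + 4 = 6 | 6 − 1 = 5 (weeks 1–5) | 6 − 1 = 5 weeks |

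The third row is an assumption, because the text does not say whether a change of band restarts the 4-week clock.

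**ALT falls below 3xULN before the persistence stop**

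No stop occurs, so no post-stop INR is triggered. The next required INR is the next scheduled draw, usually 12 or 24 weeks after the detecting draw. By then the ALT half of the criterion no longer holds. The 12 and 24 weeks are therefore not a delay in stopping. They show that a transient rise during the weekly period may never be recorded.

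**The case against.** The strongest reply is that the gap is narrow and that each case already gets individual attention.

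- The Medical Monitor must be notified within 24 hours for every participant entering increased monitoring.
- Section 7.1.1 has the investigator stop drug below the formal thresholds if that is in the participant's interest, and Appendix 3 allows additional tests at any time.
- ALT and bilirubin are still rechecked weekly and new symptoms still trigger a stop, so every other stopping criterion remains assessable.
- For harm to follow, INR must first pass 1.5 after the detecting draw, while ALT stays in range, bilirubin stays below 2xULN, no symptoms appear and the participant takes no anticoagulant. The risk table in Section 2.3.1 lists no hepatic risk for mepolizumab.
- The increased-monitoring algorithm in Section 7.1.1 is a figure that cannot be read here. Its abbreviation list includes INR, so INR may be used in it.
- The 5-week figure depends on an unstated clock restart. The table's step-down rule, which refers to 4 weeks of monitoring, fits a single clock at least as well.

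Most of this limits the size of the problem, and those limits are accepted. None of it makes INR a required weekly test. Notification, discretion and optional tests leave a mandatory stop and SAE trigger dependent on someone choosing to order the assay. The entry restriction in Section 7.1.1 keeps out anyone already meeting a criterion but requires no later INR. Reading INR into the term liver chemistries does not work either: the monitoring table spells the term out without INR, and the stopping table adds it by name. The unseen figure is a real uncertainty, but Section 7.1.1 itself sends the reader to Appendix 7 for required monitoring.

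**Conclusion.** The concern holds and should be corrected. Followed exactly, the increased-monitoring table leaves the ALT ≥3xULN with INR >1.5 stop unassessed at the weekly repeats.

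The effect is short and bounded. An INR rise present at week 1 is found about 1 week later in the higher ALT band and about 3 weeks later in the lower band. Under the clock-restart assumption with one band change, the delay is at most 5 weeks. Each figure carries a further 24 to 72 hours and assumes that no other stop intervenes. If ALT falls below 3xULN first, the rise may be missed altogether. No additional dose is attributed to the gap. The documents do not give the number of participants who would enter increased monitoring.

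Confidence is medium, because the conclusion rests on the Appendix 7 table and the Section 7.1.1 figure is not available.

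**What to change.** In the Appendix 7 increased-monitoring table, make the weekly panel ALT, AST, alkaline phosphatase, bilirubin and INR, matching the post-stop panels. Keep the anticoagulant exception in note 2. The entry criteria need no change, because Section 7.1.1 already limits this pathway to participants who meet no stopping criterion. Check that the Section 7.1.1 figure agrees.

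The text change is one analyte. As a protocol amendment it would go through the ethics approval described in Section 10.1.1 and could be bundled with other changes. The running cost is one more assay at weekly draws already required. That is 2 tests per episode if ALT stays in the higher band (weeks 1–2), 4 in the lower band (weeks 1–4), and up to 6 under the clock-restart assumption (weeks 1–6). It applies only to participants under increased monitoring and adds no visits.
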